### 209 **5.3 Subgroup Analyses**

210 To determine treatment effect heterogeneity on the study outcomes, we will use the same analytical  
211 approach as specified for the primary and secondary outcomes above but include a treatment by  
212 subgroup interaction term in the model. We will report results by the prespecified subgroups,  
213 which consists of the severity of the open fracture (Gustilo-Anderson type I or II versus type III),  
214 upper extremity versus lower extremity open fractures, and the severity of the wound  
215 contamination (none, minimal, or surface contamination versus embedded wound contamination)  
216 using a forest plot reporting odds ratios with 95% confidence intervals. These analyses will be  
217 approached and reported in accordance with best practices and guidelines for subgroup analyses.  
218  We will use the criteria suggested by Schandelmaier et al. to guide inferences about the  
219 credibility of our subgroup analyses. As participants may have more than one included fracture

220 representing different subgroups, the analyses will be performed by categorizing participants  
221 according to the fracture with the most severe injury characteristic for each subgroup.

222

223 **5.4 Sensitivity Analyses**

224 We will consider four alternative analysis approaches to evaluate the robustness of our findings,  
225 including alternative definitions of the primary outcome, an as-treated analysis of the primary and  
226 secondary outcomes, a complete case missing data analysis of the primary and secondary  
227 outcomes, and a Bayesian analysis of the primary and secondary outcomes. We will also allow  
228 for post-hoc sensitivity analysis based on information not anticipated in advance.

229

230 *Alternative Definitions of SSI:* To evaluate the robustness of the result, we will consider two  
231 alternative exploratory definitions of SSI: 1) using the confirmatory criteria from the consensus  
232 definition of Fracture-Related Infection (FRI), and 2) expanding the CDC criteria for all types of  
233 SSI to within 1 year of injury.

234

235 Our adjudication of Fracture-Related Infection is defined by the confirmatory criteria outlined in  
236 its 2018 consensus definition. The FRI criteria have been selected as an exploratory outcome  
237 because the CDC criteria have been criticized for failing to adequately account for the complexities  
238 of infections in traumatic fractures. The FRI criteria attempt to improve the ability to detect  
239 infections specifically in fracture patients; however, this definition of FRI has not been fully  
240 validated or widely adopted.

241

242 The confirmatory criteria include the presence of one or more of the following signs/symptoms:

243 1) Fistula, sinus, or wound breakdown (with communication to the bone or the implant).

244 2) Purulent drainage from the wound or presence of pus during surgery.

245 3) Phenotypically indistinguishable pathogens identified by culture from at least two separate

246 deep tissue/implant (including sonication-fluid) specimens taken during an operative

247 intervention. In the case of tissue, multiple specimens (3) should be taken, each with clean

248 instruments (not superficial or sinus tract swabs). In cases of joint effusion arising in a joint

249 adjacent to a fractured bone, fluid samples obtained by sterile puncture may be included as

250 a single sample.

251 4) Presence of microorganisms in deep tissue taken during an operative intervention, as

252 confirmed by histopathological examination using specific staining techniques for bacteria

253 or fungi.

254

255 The second exploratory definition of surgical site infection expands the CDC criteria to a 12-month

256 surveillance period. This outcome will use the same diagnostic CDC reporting criteria for the

257 primary; however, the timeframe for this outcome will be expanded to include all SSIs that occur

258 within 12 months of open fracture. Similar to the rationale for using the FRI outcome and the

259 recommendations for a minimum of 12 months follow-up for orthopaedic fracture outcomes, this

260 expanded timeframe will detect infections that occur beyond the standard CDC surveillance

261 reporting periods. This modification of the CDC reporting periods has been used in previous

262 orthopaedic fracture trials.

263

264 *As-Treated Analysis:* One of our sensitivity analyses will be performed on an as-treated population.

265 The as-treated population will include participants from the intention-to-treat population who

266 received one of the two interventions; however, participants will be classified based on the  
267 intervention received at their definitive fracture management surgery. Participants who do not  
268 receive one of the study interventions will be removed from this analysis. Similar to the primary  
269 analysis, we will use mixed effects regression models with a binomial distribution and the same  
270 covariates and correlation structure as the primary model. A more simplified structure will be  
271 considered if we encounter convergence issues with this model.

272

273 *Missing Data:* While we anticipate minimal missing outcome data, we will perform a sensitivity  
274 analysis on the primary and secondary analyses to explore the impact of missing outcome data.  
275 Our sensitivity analysis will be a complete case analysis, including only those patients with a  
276 known status of the outcome being analyzed.

277

278 *Bayesian Analysis:* The Bayesian analyses will be performed using four different priors (neutral  
279 with moderate strength, neutral flat, optimistic with moderate strength, and pessimistic with  
280 moderate strength) defined on a log-odds scale and described below. The neutral priors will be  
281 centered on a log odds of 0 (odds ratio of 1). The neutral flat prior will have a standard deviation  
282 of 100. The optimistic prior will be centered on the estimated effect size of a 0.62 odds ratio (log  
283 odds of -0.48). In contrast, the pessimistic prior is centered on the same effect size but for the  
284 alternative treatment. As suggested by Zampieri et al., the standard deviation of 0.48 was selected  
285 for the moderate strength priors as it allows for a 15% probability of the alternative treatment  
286 benefit in both the optimistic and pessimistic prior. The prior probability of our neutral prior with  
287 a moderate strength distribution implies a 68% chance the estimated effect will be between an odds

288 ratio of 0.62 and 1.38. The neutral prior with moderate strength will be our preferred prior in this  
 289 sensitivity analysis.

[figure not shown]
[figure not shown]
290

[figure not shown]
291 The modeling for the Bayesian analysis will be consistent with our primary analysis. We will use  
 292 a mixed effects regression model with a Bernoulli distribution. The model will include time and  
 293 treatment as fixed effects and use random effects to account for the complex correlation structure.

294 The best fitting correlation structure will be determined using information criteria. If we  
 295 experience convergence issues with this model structure, we will transition to a less complex  
 296 model. We will report treatment effects as odds ratios with 95% credible intervals. We will also  
 297 report the probability of treatment benefits of povidone-iodine, with 50% implying no difference  
 298 in the probability of benefit between the two treatment groups.

299

300 **Priors used in the analysis with their interpretation and a visual depiction.**

Prior	Mean	Standard Deviation	Interpretation	Visualization
Neutral with moderate strength	$\text{Log}(1.00) = 0$	0.48	“There is no strong information to suggest the intervention is good or bad in this study population, but we think extreme effect sizes are very unlikely.”	
Neutral flat	$\text{Log}(1.00) = 0$	100	“None of the prior research is relevant to this trial, and we cannot rule out extreme effect sizes.”	

301

302 **5.5 Harms**

303 The number and percentage of patients experiencing serious adverse events will be presented by  
 304 treatment arm. No formal statistical testing will be undertaken.

305

306 **5.6 Statistical Software**

307 The statistical analyses will be performed with SAS, version 9.4 (SAS Institute, Cary, NC) and R  
 308 (R Foundation for Statistical Computing, Vienna, Austria).

309

310 **6.0 FIGURES AND TABLES**311 **Table 1: Baseline characteristics**

	Iodine Povacrylex in Alcohol (n= XX participants)	Chlorhexidine in Alcohol (n= XX participants)
Age, years, mean (SD)		
Sex, n (%)		
Female		
Male		
Prefer not to answer		
Race or ethnicity, n (%)		
White		
Black		
Central or South American		
Asian		
Indigenous		
Native Hawaiian or Pacific Islander		
Multiracial		
Prefer not to answer		
Body mass index, kg/m  , n (%)		
Underweight (BMI < 18.5)		
Normal weight (18.5 – 24.9)		
Overweight (25 – 29.9)		
Obese (BMI > 30)		
Diabetes, n (%)		
Current smoker, n (%)		
Injury severity score, mean (SD)		
American Society of Anesthesiologist Physical Score, n (%)		
Class I or II		
Class III or higher		
Number of included open fractures per participant, n (%)		
One		
Two		
Three		

312

313

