4.8 Outcome Measures

4.8.1 Primary Outcome

The primary outcome is SSI, guided by the CDC's National Healthcare Safety Network reporting criteria (2017),²⁵ which includes superficial incisional SSI within 30 days and deep incisional or organ/space SSI within 90 days of fracture surgery (Table 3). Since the management of some fractures may have more than one operative procedure as part of an intentionally staged surgical plan (e.g., multiple irrigation and debridements, wound closures, temporary stabilization surgeries, definitive fixation surgery), the primary outcome will include any SSI event from the date of fracture to the end of the 30- and 90-day post-operative surveillance periods from their definitive fracture management surgery. For participants with multiple fracture regions, the date of the definitive fracture management surgery will be matched to the fracture region with the SSI.

Table 3: CDC Surgical Site Infection Criteria

Outcome	Description
Superficial Incisional SSI	
Date of event for infection occurs from the date of fracture to 30 days after the definitive fracture management surgery (where day 1 = the procedure date)
 
AND
 
involves only skin and subcutaneous tissue of the incision
 
AND
 
patient has at least one of the following:
 
 a. purulent drainage from the superficial incision. b. organisms identified from an aseptically-obtained specimen from the superficial incision or subcutaneous tissue by a culture or non-culture based microbiologic testing method which is performed for purposes of clinical diagnosis or treatment (e.g., not Active Surveillance Culture/Testing [ASC/AST]). c. superficial incision that is deliberately opened by a surgeon, attending physician or other designee and culture or non-culture based testing is not performed. 
AND

Outcome	Description

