4.8.2 Secondary Outcome

The secondary outcome is unplanned fracture-related reoperation within 12 months of the fracture(s). This outcome has been used in previous fracture trials and is defined as any unplanned surgery that occurred from the time of injury to 12 months post-injury that is associated with an infection at the operative site or contiguous to it, a wound-healing problem, or a fracture delayed union or nonunion. Common examples include any unplanned: 1) irrigation and debridement of surgical incisions or open fracture wounds due to infections or wound healing problems; 2) revision wound closure for dehiscence; 3) soft tissue coverage procedure for infected or necrotic wound; 4) fracture delayed union or nonunion surgery (such as bone grafting or implant exchange); and 5) reoperation for hardware or prosthesis failure due to infection or bone-healing problems. Removal of hardware for soft tissue prominence or periprosthetic fracture are common examples of reoperations that will not be considered outcome events. To facilitate adjudication, the treating surgeon or study personnel should take photographs of any infections or wound infections. Two orthopaedic surgeons who are members of the Adjudication Committee will independently review all reported unplanned fracture-related reoperations to determine if they meet the criteria for being a study event. The Committee will reach consensus on all reviewed unplanned fracture-related reoperations.

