4. *As-treated analyses:* The proportion of surgical procedures receiving the incorrect, non-allocated antiseptic solution will be reported. “As-treated” sensitivity analyses will be performed using the solution received as the independent variable. For participants that were treated in a single fracture surgery, they will be analyzed using the antiseptic solution received. For participants who received multiple fracture surgeries, two analyses will be performed. First, the antiseptic solution used in their last surgery prior to a study outcome event will define their study treatment. For the second analysis, the antiseptic solution received in the majority of their fracture surgeries will define their study treatment. Participants who were treated with multiple fracture management surgeries, but received equal exposure to both treatment solutions (e.g., one surgery with CHG and one surgery with iodine), will be analyzed within their originally allocated treatment group.
5. *Co-intervention variability:* Selective censoring of one or more clusters and / or treatment periods will be performed to further explore between-cluster and between-period variability identified in the primary and secondary outcome comparisons. These analyses will be used to explore the robustness of the study conclusions in the context of measured practice variations in co-interventions that differ between participating sites and / or evolve over the duration of the study recruitment. Results that are sensitive to the removal of a cluster(s) and / or period(s) will be reported, along with potential clinical hypotheses that are supported by the measured clinical practice variation.

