64 involves the final implantation of the surgical fixation hardware, when it is most susceptible to  
65 bacterial contamination and biofilm development. 2) Any open fracture surgeries prior to the  
66 definitive fracture management surgery are staged procedures to remove gross contamination,  
67 temporarily stabilize fractures in multi-trauma patients, and minimize evolving soft tissue injuries.

68 Temporally these procedures occur prior to the surgery of interest for the trial's objectives, and if  
69 bacterial contamination had occurred in one of the proceeding procedures, the repeat surgical  
70 debridement and perioperative antibiotics would reduce the likelihood of persistent occult  
71 infection occurring prior to the definitive fracture surgery.

72

73 **3.3 Analysis Populations**

74 *Intention-to-Treat*: Our primary analysis will use the intention-to-treat approach and will include  
75 all enrolled participants in the treatment groups to which their cluster was allocated at the time of  
76 their first fracture management surgery.

77

78 *As-Treated*: One of our sensitivity analyses will be performed on an as-treated population (see  
79 Section 5.4). The as-treated population will include participants from the intention-to-treat  
80 population but classified based on the intervention received at their definitive fracture management  
81 surgery. Participants who do not receive one of the two study interventions will be excluded from  
82 this analysis. This approach for defining the as-treated treatment groups is a simpler adaptation of  
83 what was initially proposed in the protocol. This final approach was selected to be consistent with  
84 the classification of adherence outlined above.

85

86

87 **4.0 TRIAL POPULATION**

88 **4.1 Cluster Screening and Eligibility**

89 Prior to commencing the trial, the investigators solicited orthopaedic surgery practices treating  
90 open fracture patients in hospitals in the United States and Canada to participate in the trial. All  
91 potential clusters completed a feasibility questionnaire prior to initiating start-up activities. To be  
92 included in the trial, each cluster had to demonstrate: 1) adequate research personnel infrastructure  
93 to manage the study, 2) adequate fracture patient volume to complete enrolment within the study  
94 timeline, 3) a commitment from all surgeons to adhere to the assigned interventions, and 4) the  

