Superficial Incisional SSI	
Date of event for infection may occur from the date of fracture to 30 days after the definitive fracture management surgery
 
AND
 
involves only skin and subcutaneous tissue of the incision
 
AND
 
patient has at least one of the following:
 
 
a. purulent drainage from the superficial incision.
 
b. organisms identified from an aseptically obtained specimen from the superficial incision or subcutaneous tissue by a culture or non-culture based microbiologic testing method which is performed for purposes of clinical diagnosis or treatment (e.g., not Active Surveillance Culture/Testing [ASC/AST]).
 
c. superficial incision that is deliberately opened by a surgeon, attending physician or other designee and culture or non-culture-based testing is not performed.
 
 
AND
 
patient has at least one of the following signs or symptoms: pain or tenderness; localized swelling; erythema; or heat.
 
 
d. diagnosis of a superficial incisional SSI by the surgeon or attending physician or other designee.
 
 
The following do not qualify as criteria for meeting the definition of superficial SSI:
 
 
• Diagnosis/treatment of cellulitis (redness/warmth/swelling), by itself, does not meet criterion "d" for superficial incisional SSI. Conversely, an incision that is draining or that
 

Outcome	Description
	
has organisms identified by culture or non-culture-based testing is not considered a cellulitis.
 
 
• A stitch abscess alone (minimal inflammation and discharge confined to the points of suture penetration).
 
• A localized stab wound or pin site infection- Such an infection might be considered either a skin (SKIN) or soft tissue (ST) infection, depending on its depth, but not an SSI
 
 
Note: A laparoscopic trocar site for an operative procedure is not considered a stab wound.
 
 
• An infected burn wound is classified as BURN and is not an SSI.
 

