Deep Incisional SSI	
The date of event for infection may occur from the date of fracture to 90 days after the definitive fracture management surgery
 
AND
 
involves deep soft tissues of the incision (e.g., fascial and muscle layers)
 
AND
 
patient has at least one of the following:
 
 
a. purulent drainage from the deep incision.
 
b. a deep incision that spontaneously dehisces, or is deliberately opened or aspirated by a surgeon, attending physician or other designee, and organism is identified by a culture or non-culture based microbiologic testing method which is performed for purposes of clinical diagnosis or treatment (e.g., not Active Surveillance Culture/Testing [ASC/AST]) or culture or non-culture based microbiologic testing method is not performed
 
 
AND
 
patient has at least one of the following signs or symptoms: fever (<math>>38^{\circ}\text{C}</math>); localized pain or tenderness. A culture or non-culture-based test that has a negative finding does not meet this criterion.
 
 
c. an abscess or other evidence of infection involving the deep incision that is detected on gross anatomical or histopathologic exam, or imaging test
 

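### The as-treated analysis reads exposure from the definitive surgery but counts events from the date of fracture, so for some staged patients exposure is measured after the outcome

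*SAP*

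**What the plan says.** Exposure. In the as-treated sensitivity analysis, section 3.3 of both the Open and the Closed SAP keeps the ITT "population but classified based on the intervention received at their definitive fracture management" surgery. Section 5.4 of both repeats the rule, classifying by the "intervention received at their definitive fracture management surgery", and applies it to the primary and secondary outcomes. Neither makes an exception for an event dated before that surgery.

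Outcome. Section 5.1 of both SAPs sets the superficial SSI window as "Date of event for infection may occur from the date of fracture to 30 days after the definitive fracture management surgery", and the deep and organ/space windows run "from the date of fracture to 90 days after the definitive fracture management surgery". Protocol 4.8.1 gives staged surgical plans as the reason: "the primary outcome will include any SSI event from the date of fracture to the end of the 30- and 90-day post-operative surveillance periods". Protocol 4.8.2 defines the secondary outcome as "any unplanned surgery that occurred from the time of injury to 12 months post-injury" that meets the listed causes.

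Change from the protocol. For participants with several surgeries, protocol 5.2.4 (item 4) planned two as-treated analyses. In the first, "the antiseptic solution used in their last surgery prior to a study outcome event will define their study treatment". The second used the solution received in most of the surgeries. Section 3.3 of both SAPs discloses that the definitive-surgery rule replaces these, and gives simplicity and agreement with the adherence definition as the reasons. Event timing is not mentioned.

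**The concern.** An as-treated comparison is informative only if the exposure comes before the outcome. Here the outcome clock starts at fracture, while exposure is read at an operation that may come later. Take a patient prepared with CHG at a first debridement, who has an SSI and is then prepared with iodine at definitive fixation. That patient enters as an infection under iodine, although the iodine could not have caused it.

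The analysis exists to show whether non-adherence drives the ITT result. It differs from ITT only through participants who received a non-allocated solution, so a classification error among them affects the very group it is meant to examine. Eligibility does not close the gap: the infection exclusions in protocol 4.2.1 and 4.2.2 apply at the initial fracture surgery only, and an infection arising between the initial and definitive operations stays in.

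**Working it through.** No figure in the documents is at issue. The first check sets the two rules side by side; the second is an illustration of size.

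**Time order**

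| Event occurs | Counted as an outcome? | Exposure read at | Exposure before outcome? |
|---|---|---|---|
| After definitive surgery | Yes | Definitive surgery | Yes |
| Between a staged procedure and definitive surgery, same solution at both | Yes | Definitive surgery | No, but the class is unaffected |
| Between a staged procedure and definitive surgery, different solutions | Yes | Definitive surgery | No, and the class is wrong |

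Only the last row does harm. It needs staged surgery, an early event and a change of solution in the same patient.

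**Size, open trial**

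Inputs from the documents: 1,540 enrolled, 10% loss to follow-up, CHG risk 12.5%, risk ratio 0.65 (protocol 5.1; Open SAP 2.3).

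- Analysable per arm: 1,540 × 0.90 / 2 = 693.
- Expected SSIs: CHG 693 × 0.125 = 86.6, taken as 87; iodine 693 × 0.08125 = 56.3, taken as 56. The total is 143.
- Planning odds ratio: (56/637) / (87/606) = 0.612.

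Assumptions, because the documents give neither share: 3 to 10% of SSIs precede definitive surgery, and 10 to 20% of those patients received the other solution at definitive surgery.

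- Low: 143 × 0.03 × 0.10 = 0.4 events.
- High: 143 × 0.10 × 0.20 = 2.9 events.
- Wider shares of 20% and 25%, with 700 per arm (144.4 events), give 144.4 × 0.20 × 0.25 = 7.2 events.

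Reclassifying moves the whole patient, so the non-event counts (637 and 606) stay fixed. If every move is from CHG to iodine:

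- 1 patient: (57/637) / (86/606) = 0.631
- 2 patients: (58/637) / (85/606) = 0.649
- 3 patients: (59/637) / (84/606) = 0.668

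The unadjusted standard error of the log odds ratio is √(1/56 + 1/637 + 1/87 + 1/606) = 0.180, which gives a 95% interval of 0.43 to 0.87. Three patients move the log odds ratio by ln(0.668/0.612) = 0.087, about 0.48 standard errors. One patient moves it by 0.16.

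**Which rule is unbiased when the solutions are equal?**

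Suppose 693 patients and 87 SSIs per arm, with 10% of SSIs (8.7) early. The switching shares below are also assumptions.

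*Switching prompted by infection.* Of the CHG patients with an early event, 20% get iodine at definitive surgery: 87 × 0.10 × 0.20 = 1.74.
- SAP rule: (88.74/606) / (85.26/606) = 1.04.
- Early-event participants left out: (78.3/606) / (78.3/606) = 1.00.

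*Switching unrelated to infection but one-way.* 3% of CHG-first patients get iodine at definitive surgery.
- SAP rule: every patient type moves in proportion, so the odds ratio is 1.00.
- Early-event participants left out: 1.00 for the same reason.
- Last surgery before the event: early events stay with CHG while event-free patients move. Iodine then has 87 + 0.03 × 78.3 = 89.35 events and 606 × 1.03 = 624.2 non-events; CHG has 84.65 and 587.8. The odds ratio is (89.35/624.2) / (84.65/587.8) = 0.994.

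Of the three rules, only leaving out early events stays at 1.00 in both patterns.

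**The case against.** The SAPs' choice is disclosed and reasoned. Open SAP 3.2 argues that the definitive operation is where the hardware is finally implanted and is the surgery of interest, and that repeat debridement and antibiotics make an infection carried over from an earlier procedure less likely. This stands as a reason to centre exposure on the definitive surgery. It does not deal with an overt event that has already been counted before that surgery.

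The practical reach is narrow, and that also stands. Protocol 4.6.2 and 4.6.7 intend staged patients to keep their initial solution even across a crossover. Protocol 4.8.1 dates an SSI when its deepest level is met, so some early superficial infections are dated later. Closed SAP 3.2 says that staged management is uncommon in closed fractures. For open fractures, protocol 1.5 says many patients need repeat debridement. The row for five or more planned surgeries in SAP Table 2 is no evidence of frequency, because it is in both SAPs' empty tables.

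A reader might infer three stronger things that the documents do not support:

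- *That the analysis is biased in a known direction by reverse causation.* No section says that solutions are changed because of infection, or more often one way than the other.
- *That the trial's main conclusion is at risk.* The primary analysis is ITT, by the cluster's allocation at the first fracture surgery, and section 3.1 of both SAPs treats sensitivity results as exploratory.
- *That restoring the protocol's rule is a clean cure.* Only the first of its two analyses respected time order; the majority rule did not. Classifying participants with an event at one surgery and those without at another makes exposure depend on outcome status, hence the 0.994 above. Loosening the rule to include surgery on the outcome date would be worse, since a reoperation's own skin preparation could then become its exposure.

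**Conclusion.** The point holds as a flaw of time order in an exploratory sensitivity analysis. From the text alone, the exposure rule and the outcome windows allow exposure to be measured after the event, and neither SAP provides for it. The size rests on the assumed shares of early events and of switched solutions, and is probably small: about 0.4 to 3 open SSIs, at about 0.02 on the odds ratio for each patient moved from CHG to iodine. Wider assumptions reach about 7 events. Moves in both directions would partly cancel. No size was worked out for the closed trial or for reoperation. The change is worth making because it is cheap and removes a doubt from the analysis meant to probe non-adherence.

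**What to change.** In sections 3.3 and 5.4 of both SAPs, keep the definitive-surgery classification and add that, for each outcome, the as-treated analysis leaves out participants whose outcome is dated before their definitive surgery, so that only outcomes after the classified exposure count. With several fracture regions, use the definitive date of the region with the event, as protocol 4.8.1 already does for SSI. State how same-day events are handled.

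Report by arm, for each outcome, how many events precede definitive surgery and how many of those participants had a different solution before and at that surgery. If the second count is zero, the SAP's current classification charged no event to a changed solution.

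The protocol's rule, with surgery strictly prior to the event, may be shown as a further check, with a note that it makes exposure depend on outcome status.

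Cost: one sentence in each SAP and light programming. Protocol 5.2.4 already plans to report the proportion of procedures given the non-allocated solution, so procedure-level data should exist. The adherence definition need not change. The downside is that a few events within the primary definition drop out of this analysis, so its outcome differs slightly from that of the ITT analysis and its result applies to participants event-free up to definitive surgery.
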